14.5.3 Analyses of Secondary and Exploratory Efficacy Endpoints

Similar analysis for the primary efficacy endpoint will be applied for other time to event efficacy endpoints.

A secondary efficacy variable, time to ready for discharge (based solely on the treating medical team's determination of GI recovery), which is defined as the time to the assessment date of "ready for hospital discharge." Length of stay is based on the time to the calendar day of discharge order written from the calendar day of surgery.

Treatment effect on other numeric variables will be analyzed using an ANOVA if normally distributed, or the Wilcoxon rank sum test otherwise. Treatment effect on categorical variables will be analyzed using the stratified Miettinen and Nurminen (M&N) method (stratified by surgical approach) ([Miettinen 1985](#)), or the logistic regression model if appropriate. Potential covariates will be identified and tested.

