9.3 Measures to Minimize Bias: Study Treatment Assignment and Blinding

9.3.1 Method of Study Treatment Assignment

Subjects will be randomized in a 1:1:1 ratio to TU-100 15 g/day, TU-100 7.5 g/day, or placebo on Day 1 before the first dose of study drug. Subject randomization will be stratified based on surgical approach, i.e., whether surgery was open or laparoscopic.

Subjects who sign an ICF will be assigned a subject number sequentially at screening. The first 3 numbers of a subject number indicate the study center and the last 4 digits indicate the order in which the subject presented to be screened (for example, Subject XXX-XXXX).

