14.2 Determination of Sample Size

The study is expected to enroll approximately 402 eligible subjects (with expected loss to follow-up or censorship of primary endpoint) with 1:1:1 randomization ratio over a post-surgery period (up to 10 days). The study is sized to achieve approximately 87% power to detect a hazard ratio (HR; TU-100 versus placebo) of 1.428 for GIR, which translates into an improvement in median time to GIR from 48 hours (2.0 days) for placebo (reference) to 34 hours (1.4 days) for TU-100 at a 0.05 significance level of one-sided log-ranked test for equality of time to GIR survival curve.

Based on historical evidence, it is assumed that a small proportion of subjects will be lost to follow-up or will have events censored due to required analytical methods. To account for this anticipated loss in contribution of events to the primary endpoint, an additional 36 subjects (approximately 10% of 366) will be enrolled to achieve a final sample size of 402 subjects (134 per group).

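### Numeric endpoints are analysed without the randomisation stratum, surgical approach; if approach is prognostic the tests are conservative and lose a few points of power

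*Combined protocol and SAP*

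**What the plan says.** Protocol Section 9.3.1: "Subject randomization will be stratified based on surgical approach", in two levels, open or laparoscopic.

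The analysis sections then treat that factor differently by type of endpoint:

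- **Time to event (14.5.2, extended to other such endpoints in 14.5.3).** Approach is a main effect in the Cox model and the stratum in the log-rank test.
- **Categorical (14.5.3).** The lead method is the "stratified Miettinen and Nurminen (M&N) method (stratified by surgical approach"). Logistic regression is offered as an alternative, with no stratum named.
- **Other numeric (14.5.3, repeated in the synopsis).** These are "analyzed using an ANOVA if normally distributed, or the Wilcoxon rank sum test otherwise". No stratum or approach term is named for either test, and no normality test, threshold or unit of assessment is given.

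Section 14.5.3 closes with a general statement that covariates may be identified and tested. It does not name approach. Section 14.1 leaves further method detail to a SAP. The text supplied contains no separate SAP section.

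**The concern.** Stratified randomisation balances the arms on approach, so differences between open and laparoscopic subjects hardly contribute to the true variance of the treatment comparison. A test that omits the stratum still counts those differences as error. Its standard error is then too large, its type I error falls below nominal, and it gives up power that the design has already bought.

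The documents suggest that approach matters for recovery. Sections 6.2.4 and 11.7 define prolonged ileus by Day 3 after minimal-incision surgery but Day 5 after open surgery.

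There is a second, separate weakness. Choosing the test from the observed distribution, with no stated criterion, lets the estimand move between a mean difference and a rank comparison, possibly in different directions for related endpoints.

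**Working it through.** **1. The plan's own figure.** Section 14.2 states "approximately 87% power to detect a hazard ratio (HR; TU-100 versus placebo) of 1.428 for GIR", "at a 0.05 significance level of one-sided log-ranked test", with 366 subjects before the loss allowance, so 122 per arm and 244 events per pairwise comparison. Schoenfeld: power = Φ(√(244/4) × ln 1.428 − 1.645) = Φ(7.810 × 0.3563 − 1.645) = Φ(1.138) = 87.2%. The stated 87% reproduces. It concerns the primary endpoint only; no SD, effect size or power is given for any numeric endpoint.

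**2. Set-up for a numeric endpoint.** From the documents: 134 per arm (Section 14.2). One-sided 0.05, which Section 14.5.1 sets for the primary endpoint, is carried over. Assumed: total SD 1; a treatment difference giving 80% power when approach has no effect; a share R² of outcome variance explained by approach.

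- SE used by the unstratified test: s = √(2/134) = 0.1222
- Difference: d = (1.645 + 0.842) × 0.1222 = 0.304
- True SE after stratified randomisation: s√(1−R²)
- Power without stratum: Φ((d − 1.645s) / (s√(1−R²)))
- Power with stratum: Φ(d / (s√(1−R²)) − 1.645)
- True alpha without stratum: 1 − Φ(1.645 / √(1−R²))

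Example, R² = 0.20: true SE = 0.1222 × 0.894 = 0.1093. Without stratum, Φ((0.304 − 0.201)/0.1093) = 82.7%. With stratum, Φ(2.780 − 1.645) = 87.2%. True alpha = 1 − Φ(1.839) = 0.033.

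| R² | Without stratum | With stratum | Loss (points) | True alpha without |
|---|---|---|---|---|
| 0 | 80.0% | 80.0% | 0.0 | 0.050 |
| 0.05 | 80.6% | 81.8% | 1.2 | 0.046 |
| 0.10 | 81.3% | 83.5% | 2.3 | 0.042 |
| 0.20 | 82.7% | 87.2% | 4.5 | 0.033 |
| 0.30 | 84.3% | 90.8% | 6.5 | 0.025 |

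**3. R² in terms of an SD difference.** If open and laparoscopic differ by δ within-stratum SDs and a fraction p is open, R² = p(1−p)δ² / (1 + p(1−p)δ²). With p = 0.30, δ = 0.5 gives 0.0525/1.0525 = 0.05 and δ = 1.0 gives 0.21/1.21 = 0.17. With p = 0.50, δ = 1.0 gives 0.25/1.25 = 0.20.

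**4. Simulation check** (4,000 runs per cell, 30% open). At R² = 0.20:

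- Normal data: ANOVA 81.8% against 86.8% with the stratum; Wilcoxon 79.5% against 84.8% for van Elteren.
- Log-normal data: Wilcoxon 81.6% against 86.6% for van Elteren.

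**5. Skewed continuous outcome, within-stratum SD held fixed** (gamma, shape 4, SD 2, treatment shift 0.6 = 0.3 SD, 30% to 50% open). Van Elteren gains about 0 points over Wilcoxon at δ = 0, about 1.5 at δ = 0.5, and 6 to 8 at δ = 1.0. The gain at δ = 1.0 exceeds the table's because total variance grows with δ here instead of being held at 1. It also depends on shape: a more skewed gamma (shape 2) gave 3 to 11 points over δ = 0.5 to 1.0.

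**6. Tied, zero-heavy counts,** the form expected for daily vomiting episodes (negative binomial; for example placebo mean 0.6, dispersion 0.6, treatment rate ratio 0.55). The gain is about 0 to 1 point at open-to-laparoscopic rate ratios of 1 to 2, and 2 to 3 points at a ratio of 3.

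**7. The normality-based choice** (Shapiro-Wilk, then ANOVA or Wilcoxon; R² = 0). Normal data: 79.6% against 79.8% for ANOVA throughout. Log-normal data: 78.6%, equal to Wilcoxon and above ANOVA at 74.8%. The choice itself loses no power.

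**The case against.** The case for leaving the sentence alone has four parts.

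**Reach.** Nearly all secondary endpoints are time-to-event or categorical. What clearly falls under the numeric sentence is exploratory eDiary counts and scores, with P values not adjusted for multiplicity. Length of stay may belong here, but Section 14.5.3 describes it as a time between calendar days and does not say which class it joins. This stands, and it limits the importance of the point.

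**Strength of the stratum.** The Day 3 and Day 5 cut-offs define a categorical complication. They do not show how far approach shifts vomiting counts or bloating scores. A reader might take the 1.0 SD result as typical, but nothing in the documents supports a difference of that size. This also stands.

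**The stratum may still enter.** The covariate statement leaves adjustment open, and the SAP may settle the method. A reader might therefore infer either that the gap is closed or that the test will still be open at unblinding. The documents establish neither. The covariate statement names no factor, a rank-sum test as written cannot carry one, and the SAP text is not available. The method stated remains unstratified.

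**Uniqueness.** A reader might infer that every other class of endpoint uses the stratum. That is too absolute, because the logistic alternative names none. A reader might also blame the normality check for lost power; step 7 shows otherwise.

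**Conclusion.** The point holds as a minor improvement. The stated numeric analyses omit the factor used to stratify randomisation, while the time-to-event analyses and the lead categorical method include it. If approach is prognostic, the numeric tests are conservative and lose power:

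- about 0 to 5 points for R² from 0 to 0.20;
- up to about 8 points at a 1.0 SD difference (shape-4 gamma);
- about 0 to 3 points for tied, zero-heavy counts;
- nothing if approach is not prognostic.

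The stratum effect, proportion open, outcome shape and treatment effect are all assumptions. The error is in the conservative direction, so no false-positive risk follows from the missing stratum. The normality-based choice is a prespecification weakness only. The primary endpoint and its 87% power are untouched.

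**What to change.** In Section 14.5.3, the synopsis and the SAP, replace the numeric sentence with one that includes surgical approach in every numeric analysis and names one method per endpoint before unblinding, in place of the normality-based choice:

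- for skewed counts and scores, a van Elteren test stratified by surgical approach;
- where a mean difference is wanted, a linear model with treatment and surgical approach.

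State whether length of stay is analysed as time-to-event or numeric. The same edit can name approach in the logistic alternative.

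One method need not be imposed on all endpoints. In particular, a Hodges-Lehmann shift should not be required everywhere: for mostly-zero counts it will often be exactly zero and says little, so the effect estimate should be chosen per endpoint. The cost is one sentence in each place and a short list of endpoints in the SAP. No subjects, visits or data are added, and at R² = 0 power is the same with or without the stratum (80.0% in both).

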14.5.4 Multiplicity Adjustments

No multiplicity adjustments are planned.

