Thus, this adequate and well-controlled Phase 2 study is designed *specifically* to directly evaluate the effect of TU-100 compared with placebo on GI recovery and other related key early in-hospital outcomes (e.g., postoperative GI-related complications, hospital LOS) following major abdominal surgery.

Details regarding known or anticipated benefits and risks, as well as reasonably anticipated AEs for TU-100 may be found in the IB.

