14.5.1 Statistical Hypotheses and Tests

The null hypothesis for the primary efficacy endpoint is that at least 1 dose regimen of TU-100 is superior to placebo with respect to the improvement in time to GIR during the post-surgery observation period (up to 10 days), which translates into a greater HR (TU-100 versus placebo).

Symbolically, the hypotheses for each dose level of TU-100 compared with placebo can be written as:

$$\begin{aligned} H_0: \text{HR} &= 1.428 \\ H_A: \text{HR} &> 1.428 \end{aligned}$$

All analyses will be performed based on 1-sided tests at the significance level of 0.05 for the primary endpoint. Nominal *P* values will be reported without any adjustment for multiple endpoints in the study.

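### The one-sided 0.05 holds for each dose separately; the at-least-one-dose superiority hypothesis it is paired with carries a false-positive rate of about 8.8%, which the plan should state or control

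*Combined protocol and SAP*

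**What the plan says.** Section 9.3.1 sets equal allocation to three arms: "Subjects will be randomized in a 1:1:1 ratio to TU-100 15 g/day, TU-100 7.5 g/day, or placebo on Day 1". Both active doses are thus compared with one shared placebo arm.

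Section 14.5.1 describes the primary hypothesis in terms of whether "at least 1 dose regimen of TU-100 is superior to placebo". It then introduces symbolic hypotheses with "the hypotheses for each dose level of TU-100 compared with placebo can be written as", which makes two tests, and adds: "All analyses will be performed based on 1-sided tests at the significance level of 0.05 for the primary endpoint". The same paragraph says that nominal P "values will be reported without any adjustment for multiple endpoints in the study"; that waiver concerns endpoints.

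Section 14.5.4 consists of one sentence: "No multiplicity adjustments are planned".

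Section 14.2 gives the sizing: "The study is sized to achieve approximately 87% power to detect a hazard ratio" of 1.428 with a one-sided log-rank test at 0.05, based on 366 subjects before the allowance for loss and 402 after it.

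The document contains no dose order, gatekeeping rule, global test or split of alpha between the doses.

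**The concern.** The level and the claim in Section 14.5.1 do not belong together. A hypothesis satisfied by either of two doses gives an ineffective product two chances to succeed, and testing each dose at 0.05 does not hold the chance of at least one success at 0.05. The waiver for multiple endpoints does not cover this, because here there are two doses on one endpoint. Section 14.5.4 says that nothing will be adjusted but does not say what the error rate of the at-least-one-dose statement then is.

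What is at stake is how the result is read. Section 5.3 presents the trial in these terms: "this adequate and well-controlled Phase 2 study is designed" to answer an efficacy question that earlier US studies left open. If one dose reaches nominal significance and the other does not, the report could declare at least one dose superior with 0.05 beside the claim, although the rate for that claim is nearly twice as high. The plan also has no agreed interpretation for such a split result.

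**Working it through.** **Inputs.** One-sided alpha 0.05 per test (14.5.1, 14.2); two dose-placebo tests (14.5.1); 1:1:1 allocation with a shared placebo arm (9.3.1); hazard ratio (HR) 1.428 and 366 contributing subjects (14.2).

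**Step 1: reproduce the plan's power.** One dose-placebo pair has 2/3 × 366 = 244 subjects. Take each as an event. With equal allocation the log-rank statistic has mean

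δ = √(244/4) × ln(1.428) = 7.810 × 0.3563 = 2.783.

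Power at one-sided 0.05 = Φ(2.783 − 1.645) = 87.2%, matching the stated 87%. A two-sided 0.05 test would give 79.5%, which does not match. The sizing therefore spends the whole one-sided 0.05 on a single dose-placebo comparison.

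**Step 2: error rate of the at-least-one-dose claim.** Assume HR = 1 for both doses. With equal arms and a common control, the two statistics have correlation of about 0.5. Then

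P(at least one false positive) = 1 − P(Z₁ < 1.645, Z₂ < 1.645) = 1 − 0.9122 = 8.78%.

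A simulation of 20 million draws gave 8.77%. The ratio to 0.05 is 8.78/5 = 1.76.

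| Correlation between tests | At least one false positive |
|---|---|
| 0.6 | 8.4% |
| 0.5 (equal arms, shared placebo) | 8.8% |
| 0.4 | 9.1% |
| 0 (independent tests) | 9.75% |

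The independence figure and the Bonferroni bound of 10% overstate the rate here because they ignore the shared placebo arm.

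**Step 3: what control at 5% would cost.** The one-sided Dunnett critical value for two doses at correlation 0.5 is 1.916 (per-dose alpha 0.0277). In step-down Dunnett the larger statistic is compared with 1.916 and, if it passes, the other with 1.645. If only one dose works, its power is about Φ(2.783 − 1.916) = 80.7%. The other entries come from the bivariate normal distribution or simulation with the same δ.

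| Rule, 244 events per pair | Both doses HR 1.428: per dose | Both doses HR 1.428: at least one | Only one dose works: power for it |
|---|---|---|---|
| Unadjusted | 87.2% | 95.4% | 87.2% |
| Step-down Dunnett | 85.1% | 91.7% | 80.7% |
| Hochberg | 85.5% | 91.9% | 79.5% |
| Fixed sequence | 87.2% first, 79.1% second | 87.2% | 87.2% if tested first, about 5% if tested second |

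Under the fixed sequence, the second dose is tested only if the first is significant. An ineffective first dose passes at most 5% of the time, and that caps power for the second.

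**The case against.** A reader might infer that the plan promises a 5% familywise error rate and breaks that promise. The document does not support this. No section states a familywise rate. The symbolic hypotheses are written per dose, Section 14.5.2 assesses TU-100 against placebo at each dose level, Section 14.2 sizes one comparison, and Section 14.5.4 is open about not adjusting. Read together, 0.05 is most naturally a per-comparison level. What remains is that Section 14.5.1 sets this level beside an at-least-one-dose hypothesis and never says which of the two it applies to.

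The at-least-one-dose wording itself sits in a garbled sentence: it is labelled the null hypothesis, and the symbols below it give H0 as HR = 1.428. That is a separate error which needs its own correction. The 8.8% assumes that HR = 1 for both doses is meant, which agrees with the test for equality of curves in Section 14.2. The document also defines no explicit trial success rule.

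A reader might further infer that an adjustment is mandatory. That does not follow. This is a Phase 2 comparison of two doses, and leaving the tests unadjusted is a legitimate trade of error control for power. The description of the trial as adequate and well controlled appears in a Phase 2 context, in contrast with earlier studies that were small, uncontrolled or not designed for this question; it does not commit the sponsor to familywise control.

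Finally, Section 14.1 says that a later SAP will supersede the protocol where they differ. No separate SAP text was available, so a later rule cannot be excluded, though Section 14.5.4 gives no sign of one.

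**Conclusion.** The concern holds as a should-fix. The one-sided 0.05 is valid for each dose-placebo comparison but is not the error rate of an at-least-one-dose claim. That rate is about 8.8%, or 8.4% to 9.1% for correlations from 0.6 to 0.4. The figure rests on HR = 1 for both doses, equal arms with a shared placebo, and the usual normal approximation for the two test statistics.

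The point does not make either dose's own P value wrong, does not show a misstated familywise rate, and does not make adjustment compulsory. The gap lies in what the plan leaves unsaid about the claim it frames.

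**What to change.** **Minimum.** State in Sections 14.5.1 and 14.5.4, and carry into the clinical study report, that 0.05 is the one-sided level per dose-placebo comparison and that a claim of superiority for at least one dose carries a false-positive rate of about 8.8%. Correct the null hypothesis in Section 14.5.1 at the same time, since the rate depends on it. This is wording only; the cost is a less favourable stated figure, with no loss of power and no added subjects.

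**If the sponsor wants 5% for the at-least-one-dose claim.** Prespecify step-down Dunnett before unblinding, at the current sample size. Restate power in Section 14.2 as about 85% per dose and 92% for at least one dose if both have HR 1.428, and about 81% instead of 87% if only one works. The loss is about 2 points per dose in the first case and 6.5 points in the second.

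**Alternatives.** Hochberg performs much the same if both doses work (about 85% per dose) but falls to about 80% if only one does. A fixed sequence keeps 87% for the dose tested first; the second has about 79% if both work and about 5% if the first is ineffective, so it suits only a sponsor with good reason for the order.

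Any of these rules must be fixed before unblinding, because a rule or dose order chosen afterwards does not control the error.

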14.6 Safety Analyses

14.6.1 Exposure to Study Medication

The total number of doses and total number of days on study drug will be summarized by treatment group. Compliance will also be summarized. Since the subjects are inpatient subjects, the compliance will only measure the compliance up to the study participation. That is, the compliance rate will not be impacted by premature discontinuation of the study.

Exposure to study medication will be summarized descriptively.

14.6.2 Adverse Events

The incidence of all TEAEs (events with onset dates on or after the start of the study drug) will be tabulated by treatment received. All reported AEs will be classified by system organ class and preferred term using the Medical Dictionary for Regulatory Activities (MedDRA). The incidence of TEAEs will be included in incidence tables. All AEs will be listed by subject, along with information regarding onset, duration, relationship and severity to study drug, action taken with study drug, treatment of event, and outcome. An overview of TEAEs, which includes subject incidence of TEAEs, treatment-related TEAEs, TEAEs by severity, SAEs, deaths, AEs leading to discontinuation, and independently adjudicated hepatobiliary AEs will be presented. Events with missing onset dates will be included as treatment-emergent. If a subject experiences more than 1 occurrence of the same AE, the occurrence with the greatest severity and the closest association with the study drug will be used in the summary tables.

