5.3 Clinical Risks/Benefits of TU-100

Risks

Evaluation of the clinical trial safety database for TU-100 involving 290 healthy volunteers and subjects with chronic GI disorders or major GI surgery revealed no apparent trends or signals with regard to hepatobiliary disorders, including DILI.

The most commonly reported AEs from completed clinical studies in healthy volunteers were headache and dyspepsia; in subjects with chronic GI disorders (including Crohn's disease, irritable bowel syndrome, and chronic constipation) were headache, nausea, back pain, and flatulence; and in surgical subjects were pruritus, vomiting, abdominal distension, and procedural pain.

Based on the totality of the evidence from post-marketing safety surveillance from Japan, no clear association between TU-100 exposure and serious liver injury is apparent at this time. The incidence of hepatobiliary ADRs is low (0.003%) and consistent over time.

Benefits

TU-100 has been evaluated across multiple patient populations and conditions within the US development program. Primary efficacy endpoints in completed US Phase 2 surgery studies were not met; however, these studies were small and uncontrolled (Study TU100P2T1) and not prospectively designed to evaluate the effect of TU-100 compared with placebo on GI recovery/POI (Studies TU100P2T1 and TU100P2T3). Thus, within this context, the question regarding potential benefit remains unanswered.

Nevertheless, there were signals that TU-100 may have improved GI recovery after colorectal resection including lower antiemetic use for nausea and numerically lower LOS compared with placebo in the Phase 2 trial of subjects undergoing laparoscopic colectomy (TU100P2T3). Moreover, in Japanese investigator-initiated trials, daikenchuto, used with varying dosing paradigms, was associated with accelerated time to first bowel movement (BM) in some patients undergoing open large BR, hepatectomy, and gastrectomy, particularly for those thought to have POI ([Katsuno 2015](#), [Kono 2019](#), [Shimada 2015](#), [Yoshikawa 2015](#)). However, due to differences in SOC and dosing regimens used in Japan compared with the US, these data must be interpreted within that context.

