12.6 Adverse Events

12.6.1 Adverse Events

An AE is any symptom, physical sign, syndrome, or disease that either emerges during the study or, if present at screening, worsens during the study, regardless of the suspected cause of the event. All medical and psychiatric conditions (except those related to the indication under study) present at screening will be documented on the medical history eCRF. Changes in these conditions and new symptoms, physical signs, syndromes, or diseases should be noted on the AE eCRF during the rest of the study. Clinically significant laboratory abnormalities should also be recorded as AEs.

Subjects will be instructed to report AEs at each study visit. All AEs are to be followed up until resolution or a stable clinical endpoint is reached. Each AE is to be documented on the eCRF with reference to date of onset, duration, frequency, severity, relationship to study drug, action taken with study drug, treatment of event, and outcome. Furthermore, each AE is to be classified as being serious or nonserious. Changes in AEs and resolution dates are to be documented on the eCRF.

For the purposes of this study, the period of observation for collection of AEs extends from the time the subject gives informed consent until the follow-up visit. Follow-up of the AE, even after the date of therapy discontinuation, is required if the AE persists until the event resolves or stabilizes at a level acceptable to the investigator.

When changes in the intensity of an AE occur more frequently than once a day, the maximum intensity for the event should be noted. If the intensity category changes over a number of days, then those changes should be recorded separately (with distinct onset dates).

The DSMB will be periodically reviewing safety data.

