14.4 Handling of Missing Data and Outliers

For incomplete date in safety data such as prior and concomitant medication and AEs, the following rules will be applied.

For partial start date:

- If the month and year are provided and day is missing, and the month and year match the month and the year of the first dose date of TU-100, the day of the first dose date of TU-100 will be imputed.
- If the year is provided and the month and day are missing and the year matches the year of the first dose date of TU-100, the month and day of the first dose date of TU-100 will be imputed. Otherwise, January will be used.
- If the start date is completely missing, the start date will not be imputed.
- If the stop date is complete and the imputed start date is after the actual stop date, then the start date will be imputed as the stop date.

For partial stop dates:

- If the month and year of stop are provided, but the day is missing, then the last day of the month will be used.
- If the year of stop is provided, but the month and day are missing, then December 31st of that year will be used.
- If the stop date is completely missing, then the date of last study visit will be used.

For laboratory test results:

- Results of a nonnumeric qualifier (e.g., “< x” – below the lower limit of quantification or “> x” – above the upper limit of quantification) will be displayed in the data listings as shown in the data, but the numerical value of “x” will be used for calculation of summary statistics.

Missing values for other data points will remain as missing unless otherwise specified. Missing values will not be imputed and only observed values will be used in data analyses and presentations unless otherwise stated. Detailed missing handling rules will be discussed in the SAP.

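### TEAEs are defined by onset date without clock time or a worsening condition, so some postoperative events that began before the first dose will be counted as treatment-emergent

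*Combined protocol and SAP*

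**What the plan says.** Section 14.6.2 defines and tabulates treatment-emergent events in one sentence: "The incidence of all TEAEs (events with onset dates on or after the start of the study drug) will be tabulated by treatment received". It sets no clock time and does not compare an event's intensity before and after dosing. It adds: "Events with missing onset dates will be included as treatment-emergent".

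Section 12.6.1 fixes what carries an onset date:

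- Collection starts early: "the period of observation for collection of AEs extends from the time the subject gives informed consent until the follow-up visit".
- The listed eCRF items include the date of onset; a time of onset is not listed.
- For changes over several days: "If the intensity category changes over a number of days, then those changes should be recorded separately (with distinct onset dates". The direction of change is not restricted.
- For changes within one day: "When changes in the intensity of an AE occur more frequently than once a day, the maximum intensity for the event should be noted".

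Section 14.4 handles partial start dates. If only the day is missing and the month and year match those of the first dose, "the day of the first dose date of TU-100 will be imputed". I read this as the first dose of study drug in any arm.

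Surgery is on Day -1. Randomization and first dose follow on Day 1, the next day (9.2, 9.3.1, 10.2.3). Table 1 schedules AE monitoring before surgery, after surgery and on Day 1.

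**The concern.** The hours between surgery and first dose lie inside AE collection and produce many symptoms that study drug cannot have caused. Section 5.3 reports that the most common AEs "in surgical subjects were pruritus, vomiting, abdominal distension, and procedural pain". Vomiting, distension and pain are what a bowel resection can be expected to produce in any arm.

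Comparing safety and tolerability with placebo is a secondary objective (6.1.2). If pre-dose symptoms enter the TEAE tables, incidence rises in every arm and the comparison carries events unrelated to treatment. A tolerability difference could then look smaller than it is. If pre-dose events enter at different rates by arm, a difference could appear where there is none.

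**Working it through.** **Step 1. Apply the written rules to typical events.**

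| Event | Onset date carried | TEAE? |
|---|---|---|
| Starts on surgery day, complete date, intensity unchanged | Day -1 | No |
| Starts on surgery day, intensity changes within that day only | Day -1, one record at maximum | No |
| Severe on surgery day, moderate on Day 1 or mild on Day 2 | New record, Day 1 or Day 2 | Yes, although improving |
| Mild on surgery day, severe on Day 2 | New record, Day 2 | Yes, and properly so |
| Starts on Day 1 before the dose | Day 1, the drug start date | Yes |
| Start day missing, month and year of first dose, no earlier stop date | First-dose date | Yes |
| Same, with a complete stop date before the first dose | Stop date (14.4) | No |
| Onset date wholly missing | None | Yes |

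Two routes misclassify events with complete dates: pre-dose onset on Day 1, and improvement dated on or after the first-dose date. The two date rules add to them.

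The laboratory case shows the conflict. Day 1 samples are drawn before dosing and serve as baseline (10.2.3, 14.1). A clinically significant result is an AE (12.5, 12.6.1). The same sample can therefore be a subject's baseline and a TEAE.

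**Step 2. Size if pre-dose events enter equally in all arms.** The documents give no TEAE rates, so there is no planned figure to reproduce and every input here is an assumption. Let p be the true post-dose incidence and a the share of subjects counted through a pre-dose event, equal across arms and independent of p.

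Observed incidence = a + (1 − a)p

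Observed risk difference = (1 − a)(p_active − p_placebo)

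For assumed true rates of 10% on placebo and 20% on active:

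| a | Placebo | Active | Difference (points) | Risk ratio |
|---|---|---|---|---|
| 0 | 10.0% | 20.0% | 10.0 | 2.00 |
| 5% | 14.5% | 24.0% | 9.5 | 1.66 |
| 10% | 19.0% | 28.0% | 9.0 | 1.47 |
| 20% | 28.0% | 36.0% | 8.0 | 1.29 |
| 30% | 37.0% | 44.0% | 7.0 | 1.19 |
| 50% | 55.0% | 60.0% | 5.0 | 1.09 |

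As a yardstick only, since no test of TEAEs is planned: with 134 per arm and two-sided 0.05, power for this contrast is 63% at a = 0, 51% at 5%, 41% at 10% and 29% at 20%.

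**Step 3. Size if they enter unequally.** Randomization takes place on Day 1 before the first dose, so the prevalence of pre-dose events should balance. Re-dating through an intensity change can happen after treatment starts and so may depend on arm. Assume 10% true incidence in both arms, 40% of subjects with a pre-dose event, and a share q of those events re-dated.

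Observed incidence = 0.40q + (1 − 0.40q) × 0.10

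- q = 0.5 on placebo: 0.20 + 0.80 × 0.10 = 28.0%
- q = 0.7 on active: 0.28 + 0.72 × 0.10 = 35.2%

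The spurious difference is +7.2 points; with the two values of q exchanged it is −7.2. The direction cannot be predicted. Faster easing can create more post-dose records, but an event that resolves outright, without passing through a milder category, creates none.

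**The case against.** The case for leaving the rule alone has five parts.

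- **Inclusive counting looks deliberate.** Missing and partial dates are resolved toward TEAE, which avoids discarding ambiguous Day 1 events. That is a fair reason to keep events of unknown timing. It does not justify counting an event known to precede the dose, or one known to have improved.
- **Medical history may absorb these events.** Section 12.1 extends history to conditions ongoing up to first dosing. But 12.6.1 and Table 1 collect AEs throughout that period, so 12.1 conflicts with them and does not settle the matter.
- **The SAP and eCRF may handle it.** Section 14.1 lets the SAP supersede the protocol, and the eCRF is not shown, so an onset-time field may exist. No SAP text in the documents changes the rule, and an SAP cannot recover a time that was not collected.
- **Other data cover the ground.** The eDiary records nausea, vomiting and bloating by day, laboratory data have shift tables, and hepatobiliary risk rests on blinded adjudication (11.3, 14.6.4, 14.7.1). All AEs are also listed with onset. These limit the harm but leave the general TEAE tables uncorrected.
- **The tables are descriptive.** This stands: no test is planned, so the power figures are only a yardstick.

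A reader might infer that every intensity change gets a new onset date and that pre-dose postoperative events generally become TEAEs. The text does not support that. Changes within a day stay in one record, a surgery-day event with a complete date and stable intensity stays out, and worsening after the dose is rightly counted.

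**Conclusion.** The point holds for a defined subset: Day 1 onsets before dosing, and pre-dose events whose intensity category changes on or after the first-dose date without worsening after the dose. The missing-date and partial-date rules push further events the same way. TEAE incidence is inflated. Differences between arms may be diluted, or distorted if symptoms ease at different speeds by arm.

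The size is unknown. The share a, the event rates and the re-dating shares above are all assumed; at a = 5% the loss in risk difference is half a point, at 50% it is five points. A reader might conclude that the rule hides real differences between arms. The documents do not show that: dilution is the expected direction only if misclassification is equal across arms. The change is still worth making, because the flaw follows from the wording and the correction is cheap.

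**What to change.** 1. In 14.6.2, define a TEAE as an event with onset after the date and time of the first dose, or an event present before the first dose that worsens in intensity after it.
2. Add an eCRF field, before or after first dose, for AEs with onset on Day 1. Dosing time is already recorded (10.2.3). Events of unknown timing stay TEAEs, so the missing-date and partial-date rules can remain as a conservative fallback.
3. In 12.6.1, link each intensity-change record to its parent event and state that a decrease in intensity does not create a new TEAE.
4. List events from surgery to first dose separately as pre-treatment postoperative events.
5. Reconcile 12.1, which takes medical history up to first dosing, with AE collection from consent.

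The cost is one eCRF field, the record link if the eCRF lacks one, and protocol and SAP wording. TEAE counts will be somewhat lower in all arms. No visits or subjects are added. The field must be in place before the events are recorded.
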